9.10. Data Management

Participant data are recorded on data forms. Investigators and study personnel at the VRCC) are responsible for the integrity of the data (i.e., accuracy, completeness, legibility, and timeliness) reported to the sponsor.

Paper/electronic data collection forms will be used to capture study-specific participant data. Instructions for completion and correction of data collection forms will be provided.

Appropriate measures such as encryption or deletion must be enforced to protect the identity of participants when transmitting data, in all presentations and publications as required by local/regional/national requirements.

For electronic case report forms: The system for electronic data capture (EDC) and support services will be Medidata Rave.

An audit trail will be maintained in the EDC application containing as a minimum: identification of the person entering the data, date and time of the entry and reason for the correction, the original entry, and the corrected entry.

To enable evaluations and/or audits from regulatory authorities or the study sponsor, the investigator agrees to keep records, including the identity of all participating patients, all original signed consent to release information, copies of all electronic case report forms (eCRFs), serious adverse event (SAE) forms, source documents, and adequate documentation of relevant correspondence. The records should be retained by the investigator according to local regulations or as specified in the study-specific site contract, whichever is longer.

9.11. Data Analysis

Analyses will be conducted by PPD in accordance with the study objectives, statistical analysis plan (SAP), table/listing shells, and applicable guidelines. Data analyses will be performed with SAS® statistical software (version 9.4 or higher, SAS Institute, Cary, NC). Additional details will be provided in the SAP.

To minimize the potential impact of bias, adjusted analyses (Section 9.11.2.4), stratified analyses (Section 9.11.2.5), supplementary analyses (Section 9.11.2.6), and sensitivity analyses (Section 9.11.2.7) will be performed.

[figure not shown]
9.11.1. Definition of Analysis Sets

9.11.1.1. Analysis Population

As depicted in [Figure 9.2](#), the main analysis population will include participants who:

- Are valid (Section 9.11.1.1.1)
- Had a qualifying diagnosis at the time of prescribing (Section 9.11.1.1.2)
- Are prospectively enrolled (Section 9.11.1.1.3)
- Are not exposed to teratogens or investigational medications or congenital infectious agents during pregnancy (Section 9.11.1.1.4)
- Are not considered lost to follow-up (Section 9.11.1.1.5)
- Are not already included in the analysis population for a prior pregnancy (Section 9.11.1.1.6), and
- Among the tirzepatide exposed cohort, have not been exposed to other GLP-1 RA therapies during pregnancy or within 5 times the half-life of the drug prior to conception.

For the analyses of preterm birth, SGA, postnatal growth deficiency, rapid infant weight gain, and infant developmental delay, multiple gestation pregnancies will be excluded from the analysis population.

Abbreviation: HCP = healthcare professional; GLP-1 RA = glucagon-like peptide-1 receptor agonist.

Figure 9.2. Attrition diagram.

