9.5.2. Inclusion and Exclusion Criteria

For an eligible participant, all inclusion criteria must be answered ‘yes’, and all exclusion criteria must be answered ‘no’. Table 9.1 summarizes the inclusion and exclusion criteria for the cohorts.

[figure not shown]
Table 9.1. Study Population

Cohort	Inclusion Criteria ^a	Exclusion Criteria ^a
Tirzepatide exposed cohort: A cohort of individuals who are treated with tirzepatide for weight management during pregnancy ^{b,c,d}	
 Signed consent obtained before any study-related activities AFAB 15-≤50 years of age at the time of signing consent Currently or recently (within 12 months) pregnant Resident of country included in the study Authorization for their HCP(s) to provide data to the registry Exposure to at least one dose of tirzepatide for weight management at any time during pregnancy^{b,c} Prescribed the qualifying AOM for treatment of obesity^e or overweight with at least one weight-related comorbid condition^f 	
 None^{c,d}
AOM active comparator cohort: A cohort of individuals who are treated with pharmacotherapy other than tirzepatide or other therapies with GLP-1 RA activity for weight management during pregnancy. ^b The comparator AOMs may include, but are not limited to, orlistat, setmelanotide, and naltrexone-bupropion	
 Signed consent obtained before any study-related activities AFAB 15-≤50 years of age at the time of signing consent Currently or recently (within 12 months) pregnant Resident of country included in the study Authorization for their HCP(s) to provide data to the registry Exposure to at least one dose of AOM other than tirzepatide or other therapies with GLP-1 RA activity at any time during pregnancy^d Prescribed the qualifying AOM for treatment of obesity^e or overweight with at least one weight-related comorbid condition^f 	
 Exposure to tirzepatide or other therapies with GLP-1 RA activity at any time during pregnancy^b

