AOM unexposed comparator cohort: A cohort of individuals who have obesity or are overweight with at least one weight-related comorbid condition at the time of conception and who are not treated with tirzepatide, GLP-1 RA therapies, or any other approved products for weight management, during pregnancy ^b	
 Signed consent obtained before any study-related activities AFAB 15-≤50 years of age at the time of signing consent Currently or recently (within 12 months) pregnant Resident of country included in the study Authorization for their HCP(s) to provide data to the registry Have obesity^f or overweight with at least one weight-related comorbid condition^g at time of conception 	
 Exposure to tirzepatide or other therapies with GLP-1 RA activity at any time during pregnancy^b Exposure to any other pharmacotherapies for weight management^e at any time during pregnancy^b

Abbreviations: AFAB = assigned female at birth; AOM = anti-obesity medication; BMI = body mass index; DOC = date of conception; GLP-1 RA = glucagon-like peptide-1 receptor agonist; HCP = healthcare provider; LMP = last menstrual period; VRCC = virtual registry coordination center

- ^a Text italicized to highlight differences between cohorts.
- ^b Participants will be considered exposed to tirzepatide or other therapies with GLP-1 RA activity or other products during pregnancy if a dose is taken up to 5 half-lives prior to the DOC (LMP + 14 days). Participants who are exposed to tirzepatide or other therapies with GLP-1 RA activity before pregnancy, but more than the 5 half-lives prior to DOC may be eligible for enrollment into the comparator cohort, if they fulfil certain eligibility criteria.
- ^c Individuals prescribed tirzepatide for reasons other than weight management can be enrolled into the current study, but they are not the focus of the current protocol and will be excluded from the main analysis population (see Section 9.11.1.2).
- ^d In some countries, only patients prescribed tirzepatide according to the approved indications may be included, in accordance with local regulations.
- ^e Eligible comparator medications at this time include orlistat, setmelanotide, and naltrexone-bupropion. Newly approved medications will be reviewed regularly and added if applicable.
- ^f Obesity defined as: BMI ≥ 30 kg/m²

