- ^g Overweight defined as BMI ≥ 27 kg/m² and at least one weight-related comorbid condition (e.g., hypertension, dyslipidemia, type 2 diabetes mellitus, obstructive sleep apnea, or cardiovascular disease).

The study aims for inclusive enrollment by incorporating only inclusion criteria common for observational studies, with minimal exclusion criteria. To address potential biases and confounding, the main analysis population for the study will be further limited to individuals who are prospectively enrolled (prior to pregnancy outcome), not exposed to known teratogens and/or investigational medications during pregnancy, not exposed to other GLP-1 RA therapies during pregnancy or within 5-times the half-life of the drug prior to conception, not lost to follow-up, and not already included in the analysis population for a prior pregnancy. The definitions of the main analysis population and the rationale are provided in Section 9.11.1.1.

^a Time to product elimination (5 times terminal half-life); tirzepatide half-life = 5 days; therefore, time to elimination = 25 days

^b If a participant is exposed to the product during this period, they will be considered exposed during pregnancy

^c Participants may be retrospectively enrolled into the registry up to one year after pregnancy outcome but will not be included in main analysis

Figure 9.1. Study flow chart.

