9.7. Variables

9.7.1. Exposure Definitions and Ascertainment

Exposure to tirzepatide is a condition for inclusion into the exposed cohort. Exposure is defined as bodily uptake of any dose of tirzepatide at any time during pregnancy (from conception to pregnancy outcome) or prior to pregnancy (within a specified time based on the product's half-life). Due to the half-life of tirzepatide (approximately 5 days), tirzepatide is likely to be eliminated from the body within 5 half-lives (25 days or 3.5 weeks). Therefore, individuals exposed to tirzepatide within ≤ 25 days of DOC will be considered exposed. Individuals in the tirzepatide cohort who are exposed to other GLP-1 RA therapies during pregnancy or within 5 times the half-life of the drug prior to conception will be excluded from the main analysis to prevent class effect interactions. However, they may still be enrolled into the study as part of the tirzepatide exposed cohort.

Exposure to comparator products for weight management is defined as bodily uptake of any dose of a qualifying product for weight management at any time during pregnancy (from conception to pregnancy outcome) or prior to pregnancy (within 5-half-lives of DOC). Detailed information on drugs for weight management and their respective exposure windows are detailed in Drugs of Interest for Cohort Eligibility.

Detailed information on dose, route, frequency, dates/duration of exposure, and indication/reason for use will be collected, and exposure will be further categorized by earliest trimester of exposure. Section 9.7.5 provides information on the methods used to determine gestational age and trimester of exposure.

Exposure information will be updated at each pregnancy follow-up and changing exposures will be accounted for in the analysis. For example, if a pregnant individual was enrolled into the comparator cohort but later during pregnancy became exposed to tirzepatide, for the analysis they would be included in the tirzepatide exposed cohort.

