9.11.2.6. Supplementary Analyses

Supplementary descriptive analyses of all outcomes will be conducted as specified for the main analysis population but that include pregnant individuals who were excluded from the main analysis population due to:

- Occurrence of the pregnancy outcome prior to enrollment (retrospectively enrolled participants)
- Exposure to a known teratogen or an investigational medication during or prior to pregnancy (teratogen/investigational medication-exposed participants)
- Exposure to other GLP-1 RA therapies during pregnancy or within 5 times the half-life of the drug prior to conception among the tirzepatide exposed cohort
- Treatment with tirzepatide during pregnancy for reasons other than weight management among the tirzepatide-exposed cohort
- Inclusion of a prior pregnancy in the analysis population (subsequent pregnancies)

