- Sensitivity analyses will also be conducted to assess the potential impact of missing data and/or unmeasured confounding (e.g., quantitative bias analysis to estimate the overall strength of potential unmeasured confounding required to nullify the estimated treatment effect or reverse the statistical inference).¹⁰⁸
- A sensitivity analysis will be conducted that limits the tirzepatide exposed and the AOM active comparator cohorts to individuals with a diagnosis of obesity, or overweight with at least one weight-related comorbid condition at the time of conception.
- A sensitivity analysis will be conducted that expands the tirzepatide exposed cohort to individuals exposed to any other weight loss medications (including GLP-1 RAs) other than tirzepatide.
- In the main analysis, maternal use of within 5 half-lives of the respective medication is defined as a potential fetal exposure to medication use during pregnancy. This is a conservative estimate which may dilute a potential association between medication and the study outcomes. Sensitivity analysis will be conducted with shorter half-lives (i.e., 1-, 2- and 3-times half-lives) to define fetal exposure to medication use during pregnancy.
- Pregnant individuals who are exposed to a known teratogen or an investigational medication during or prior to pregnancy will be excluded from the main analysis population and described in the supplementary analyses. In the case that there are more than 10% of pregnant individuals with teratogen exposure during or prior to pregnancy, an additional sensitivity analysis will be considered by retaining those individuals in the analysis and addressing potential impact of teratogen exposure via analytical adjustment. More details will be included in the SAP.

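### The main analysis keeps women who took both tirzepatide and a non-GLP-1 comparator drug in the tirzepatide arm, and the sensitivity analysis meant to expand that arm does not fit this rule

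*Protocol*

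**What the plan says.** - **Eligibility (Section 9.5.2, Table 9.1).** The tirzepatide cohort has no exclusion criterion. The active comparator cohort excludes "Exposure to tirzepatide or other therapies with GLP-1 RA activity at any time during pregnancy". A footnote names the comparator drugs: "Eligible comparator medications at this time include orlistat, setmelanotide, and naltrexone-bupropion". Section 7.4.3 classes all three as non-GLP-1 drugs.
- **Main analysis population.** Section 9.11.1.1 requires "Among the tirzepatide exposed cohort, have not been exposed to other GLP-1 RA therapies during pregnancy or within 5 times the half-life". Section 9.5.2 has the same limit: "not exposed to other GLP-1 RA therapies during pregnancy or within 5-times the half-life of the drug prior to conception". Section 9.7.1 repeats it and gives possible class-effect interactions as the reason.
- **Changing exposure (Section 9.7.1).** The worked example is a participant enrolled in the comparator cohort who "later during pregnancy became exposed to tirzepatide, for the analysis they would be included in the tirzepatide exposed cohort".
- **Supplementary analyses (Section 9.11.2.6).** The list of excluded groups brought back for description includes "Exposure to other GLP-1 RA therapies during pregnancy or within 5 times the half-life of the drug prior to conception among the tirzepatide exposed cohort". It has no entry for co-exposure to non-GLP-1 weight-management drugs.
- **Sensitivity analyses (Section 9.11.2.7).** One analysis "expands the tirzepatide exposed cohort to individuals exposed to any other weight loss medications (including GLP-1 RAs) other than tirzepatide".

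**The concern.** The overlap between the two treated cohorts is handled on one side only. A woman with both exposures cannot be in the active comparator cohort, but nothing removes her from the tirzepatide cohort. Comparison #1 is presented as tirzepatide against other anti-obesity drugs, yet its tirzepatide arm may contain those same drugs. In Comparison #2 the unexposed cohort has no such drug by definition, so any effect of the co-medication is counted as a tirzepatide effect. Both comparisons carry the primary outcome, major congenital malformations (MCM).

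Propensity weighting does not remove the problem. Every active comparator participant has the comparator drug and no unexposed participant has it, so there is no overlap on which to balance this exposure.

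The sensitivity analysis in Section 9.11.2.7 is the natural place to see how much dual use matters. For non-GLP-1 drugs taken with tirzepatide it would return the same women as the main analysis.

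**Working it through.** **Passages side by side**

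| Woman's exposures | Active comparator cohort | Tirzepatide arm, main analysis | In the 9.11.2.6 list | Added by the 9.11.2.7 analysis |
|---|---|---|---|---|
| Tirzepatide + other GLP-1 RA | Barred | Removed | Yes | Yes |
| Tirzepatide + orlistat, setmelanotide or naltrexone-bupropion | Barred | Kept | No | Nobody to add |

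The sensitivity analysis covers any other weight loss medication and names GLP-1 RAs as a subset. Under the main rule, that subset is the only part that can add tirzepatide users.

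**The plan's own figures.** Section 9.9.1 uses 3% against 9% (relative risk 3), two-sided alpha 0.05, 80% power and 1:1 allocation, with the Walters approximation to Fisher's exact test:

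power = Φ{[arcsin√(p₂ − 1/(2n₂)) − arcsin√(p₁ + 1/(2n₁))] × √(4n₁n₂/(n₁+n₂)) − 1.96}

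With n₁ = n₂ = 265 this gives 80.1%, and 265 is the smallest n reaching 80%. Enrolment is 265/(0.9 × 0.9 × 0.9) = 363.5, so 364. Both stated figures reproduce.

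**Effect on the estimates.** The notation is:
- t: relative risk of tirzepatide against no drug;
- c: relative risk of the comparator drug against no drug;
- p: share of dual users in the tirzepatide arm;
- r: risk with no drug.

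Effects are assumed multiplicative.

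- Tirzepatide arm risk: r[(1 − p)t + p·t·c] = r·t·[1 + p(c − 1)]
- Comparison #1: (t/c) × [1 + p(c − 1)], where t/c is the value without dual users
- Comparison #2: t × [1 + p(c − 1)], where t is the value without dual users

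The protocol gives neither p nor c, so the values below are assumptions.

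| t | c | p | #1 without → with dual users | #2 without → with dual users |
|---|---|---|---|---|
| any | 1 | any | no change | no change |
| 1 | 2 | 5% | 0.50 → 0.53 | 1.00 → 1.05 |
| 1 | 2 | 20% | 0.50 → 0.60 | 1.00 → 1.20 |
| 3 | 1.5 | 10% | 2.00 → 2.10 | 3.00 → 3.15 |
| 3 | 2 | 10% | 1.50 → 1.65 | 3.00 → 3.30 |
| 3 | 2 | 20% | 1.50 → 1.80 | 3.00 → 3.60 |

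For p = 10%, c = 2 and t = 3 the factor is 1 + 0.10 × (2 − 1) = 1.10. Then 1.50 × 1.10 = 1.65 and 3.00 × 1.10 = 3.30. When c exceeds 1 the estimate always rises: toward the null if t/c is below 1, away from it if t/c is above 1.

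**Cost of excluding dual users.** Put n₂ = 265(1 − p) in the power formula and keep n₁ = 265. Enrolment needed to hold 265 live births is 265/0.729/(1 − p).

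| p (assumed) | Power at relative risk 3, not replaced | Tirzepatide enrolment to keep 265 |
|---|---|---|
| 5% | 79.0% | 383 |
| 10% | 77.7% | 404 |
| 20% | 74.8% | 455 |

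**The case against.** The strongest defence is that the rule is a deliberate choice. Section 9.7.1 explains the GLP-1 RA exclusion by class effects, a reason that does not reach non-GLP-1 drugs, and Section 9.5.2 favours inclusive enrolment. Treating any tirzepatide exposure as tirzepatide exposed is a coherent hierarchy. That stands as a possible estimand, but the protocol does not state it for Comparison #1, and it leaves the sensitivity analysis without content for these drugs.

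Other points limit the size of the concern:

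- Dual use may be rare. Section 7.4.3 says patients are advised to stop tirzepatide when pregnancy is recognised, and Section 9.9.2 assumes 95% discontinuation.
- The switching example in Section 9.7.1 does not say which comparator cohort it means. A late switch drops out of the MCM analysis, which requires first-trimester exposure.
- A co-drug on the teratogen list would be removed under Section 9.11.1.1.4. That list is a standalone document and is not a general exclusion of comparator drugs.
- Section 9.7.4 lists other drug exposure as a possible covariate, and Section 9.11.2.4 allows regression adjustment for residual imbalance. In Comparison #2 a co-drug term could be estimated. In Comparison #1 it would change the contrast to tirzepatide added to comparator drug, so it does not restore the drug-against-drug comparison.

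A reader might infer three stronger things that the protocol does not support:

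- **That the sensitivity analysis shows dual users were meant to be excluded.** This is only an inference from its wording. The sentence could also mean adding women who took other drugs without tirzepatide, which fits the cohort definitions no better.
- **That the drug difference is always diluted.** At the relative risk of 3 used for sizing, with c = 2, Comparison #1 moves away from the null.
- **That a bias of known size exists.** The rules permit overlap; they do not say how often it occurs.

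**Conclusion.** The point holds as a gap in the analysis-set definition and a mismatch between sections. Sections 9.5.2, 9.7.1 and 9.11.1.1 leave non-GLP-1 co-users in the tirzepatide arm, Section 9.11.2.6 does not count them as excluded, and Section 9.11.2.7 describes an expansion that cannot add them. The distortion is a factor of about 1 + p(c − 1) in both comparisons, under multiplicative effects. It is nil if the comparator drug carries no risk and 1.10 at the illustrative p = 10% and c = 2. Both values are assumptions, and the direction relative to the null depends on the true relative risk. The sample-size figures are correct and not in dispute. Because the main analysis population is fixed in the protocol, the matter should be settled there.

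**What to change.** 1. In Section 9.11.1.1, and to match in Sections 9.5.2 and 9.7.1 and Figure 9.2, extend the main-analysis exclusion for the tirzepatide cohort from other GLP-1 RAs to any other weight-management pharmacotherapy taken within its exposure window.
2. Add these women to the list in Section 9.11.2.6.
3. Keep the Section 9.11.2.7 analysis as the place where they re-enter, reworded as tirzepatide users who also took another weight loss medication.
4. Name this reason in the 10% exclusion allowance of Section 9.9.1, which does not mention it.

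If the sponsor prefers to keep dual users in, the protocol should say so and turn the sensitivity analysis into one that leaves them out.

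The exclusion needs one flag from exposure data already collected (Section 9.8). The cost is a loss of exposed participants, small if dual use is uncommon, with the power and enrolment consequences tabulated above. It matters because Section 9.9.2 already projects only 305 exposed women against a target of 364.

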9.11.1.1.1. Valid Versus Invalid Participants

A valid participant is defined as a pregnant individual with sufficient data, submitted or confirmed by an HCP, for determining inclusion/exclusion into one of the study population cohorts (Section 9.5.2). Participants who lack the minimum data required for determining inclusion/exclusion into one of the study cohorts or who lack confirmation from an HCP will be considered invalid. Invalid participants will be enumerated in each registry report but will not be included in statistical analyses.

9.11.1.1.2. Treatment with Tirzepatide during Pregnancy for Indications Other Than Weight Management

The focus of the current study is limited to exposures to tirzepatide prescribed for the treatment of obesity or overweight with at least one weight-related comorbid condition. Therefore, individuals prescribed tirzepatide for indications other than weight management (e.g., type 2 diabetes) can be enrolled into the current study, but they will be excluded from the main analysis population. The main analysis population will only include participants treated for obesity or overweight with at least 1 weight-related comorbid condition. Individuals meeting the criteria for

enrollment who also have comorbid type 2 diabetes are eligible for inclusion in the main analysis population.

